### 9.3. ANALYSIS VISITS

#### Time windows

Except for ECG baseline, if two or more assessments are performed within a time window then the assessment closest to the planned visit is used in analyses by time window. For worst post-baseline assessment all on-treatment values are considered regardless of time windows.

Time windows for criteria are defined in Table 2 to Table 7.

**Table 2: Time windows for weight, ECOG PS, ophthalmic and dermatological examination, ECHO/MUGA, coagulation, urinalysis, EORTC QLQ-C30; EQ-5D-5L, PGIC**

Time Window	Planned Visit Timing	Time Window Definition
Baseline	Study day 1 pre-dose	Before first study treatment administration
Cycle 2 Day 1	Study day 29	Study day 1 post-dose to 43
Cycle x Day 1	Study day $(x-1)*28+1 = k$	Study days $k-13$ to $k+14$
Safety follow-up	Post treatment study day 30*	Last administration of study treatment day+1 to Post treatment study day 37

\* Study day  $i =$  First day of study treatment administration +  $(i-1)$  day(s)

Post treatment study day  $i =$  Last administration of study treatment day +  $i$  day

**Table 3: Time windows for vital signs**

Time Window	Planned Visit Timing	Time Window Definition
Baseline	Study day 1 pre-dose	Before first study treatment administration
Up to week 28		
Cycle 1 Day 8	Study day 8	Study days 1 post dose to 11
Cycle 1 Day 15	Study day 15	Study days 12 to 18
Cycle 1 Day 22	Study day 22	Study days 19 to 25
Cycle 2 Day 1	Study day 29	Study days 26 to 32
Cycle x Day y (except CID8)	Study day $(x-1)*28+y = k$	Study days k-3 to k+3
From week 29 (Cycle 8 Day 1)		
Cycle 8 Day 1	Study day 197	Study days 194 to 204
Cycle 8 Day 15	Study day 211	Study days 205 to 218
Cycle 9 Day 1	Study day 225	Study days 219 to 233
Cycle x Day y from cycle 8 Day 15	Study day $(x-1)*28+y = k$	Study days k-6 to k+7
Safety follow-up	Post treatment study day 30	Last administration of study treatment day+1 to Post treatment study day 37

\* Study day  $i =$  First day of study treatment administration +  $(i-1)$  day(s)  
 Post treatment study day  $i =$  Last administration of study treatment day +  $i$  day

**Table 4: Time windows for ECG**

Time Window	Planned Visit Timing	Time Window Definition
Baseline	Study day 1 pre-dose	Before first study treatment administration
Cycle 1 Day 1 post-dose	Study day 1 post-dose	Study days 1 post dose to 8
Cycle 1 Day 15	Study day 15	Study days 9 to 22
Cycle 2 Day 1 pre-dose	Study day 29 pre-dose	Study days 23 to before C2D1 study treatment administration
Cycle 2 Day 1 post-dose	Study day 29 post-dose	Study days 29 C2D1 post dose to 43
Cycle x Day 1 from cycle 3	Study day $(x-1)*28+1 = k$	Study days $k-13$ to $k+14$
Safety follow-up	Post treatment study day 30*	Last administration of study treatment day+1 to Post treatment study day 37

\* Study day  $i =$  First day of study treatment administration +  $(i-1)$  day(s)  
 Post treatment study day  $i =$  Last administration of study treatment day +  $i$  day

**Table 5: Time windows for hematology**

Time Window	Planned Visit Timing	Time Window Definition
Baseline	Study day 1 pre-dose	Before 1rst administration
Cycle 1 Day 15	Study day 15	Study day 1 post-dose to 18
Cycle 1 Day 22	Study day 22	Study days 19 to 25
Cycle 2 Day 1	Study day 29	Study days 26 to 43
Cycle x Day 1 from cycle 3	Study day $(x-1)*28+1 = k$	Study days k-13 to k+14
Safety follow-up	Post treatment study day 30*	Last administration of study treatment day+1 to Post treatment study day 37

\* Study day  $i =$  First day of study treatment administration +  $(i-1)$  day(s)

Post treatment study day  $i =$  Last administration of study treatment day +  $i$  day

**Table 6: Time windows for chemistry**

Time Window	Planned Visit Timing	Time Window Definition
Baseline	Study day 1 pre-dose	Before 1rst administration
Cycle 1 Day 1	Study day 1 post-dose	Study days 1 post dose to 8
Cycle 1 Day 15	Study day 15	Study days 9 to 22
Cycle 2 Day 1	Study day 29	Study days 23 to 43
Cycle x Day 1 from cycle 3	Study day $(x-1)*28+1 = k$	Study days k-13 to k+14
Safety follow-up	Post treatment study day 30*	Last administration of study treatment day+1 to Post treatment study day 37

\* Study day  $i =$  First day of study treatment administration +  $(i-1)$  day(s)  
 Post treatment study day  $i =$  Last administration of study treatment day +  $i$  day

**Table 7: Time windows for CEA, CA19-9**

Time Window	Planned Visit Timing	Time Window Definition
Baseline	Study day 1 pre-dose	Before 1rst administration
Cycle 2 Day 1	Study day 29	Study days 1 post dose to 43
Cycle x Day 1 from cycle 3	Study day $(x-1)*28+1 = k$	Study days k-13to k+14
Safety follow-up	Post treatment study day 30*	Last administration of study treatment day+1 to Post treatment study day 37

\* Study day  $i =$  First day of study treatment administration +  $(i-1)$  day(s)  
 Post treatment study day  $i =$  Last administration of study treatment day +  $i$  day

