9.1.9. End-of-Treatment Visit _ Main study period

At the time of study treatment discontinuation, the EOT visit should be completed for all subjects as soon as possible after the last dose of study drug, and every effort should be made to perform the procedures listed below. This visit should take place as soon as possible and ≤ 14 days after the last dose of study treatment. An e-CRF should be completed, giving the date and reason for stopping the study treatment. All subjects will enter the follow-up period

If a subject withdrawal occurs or if the subject fails to return for visits, the Investigator must determine the primary reason for a subject's discontinuation from the study and record this information on the relevant page of the e-CRF.

Subjects will be assessed for the following:

- QOL questionnaires (EORTC QLQ-C30, EQ-5D-5L, PGIC)

- Physical examination including weight
- Full ophthalmic examination
- Vital signs (blood pressure, pulse, temperature and respiratory rate)
- ECOG PS
- Single ECG
- Dermatologic examination
- ECHO/MUGA
- Serum pregnancy test (for females of childbearing potential only)
- Collection of blood samples for:
 - Hematology, coagulation and clinical chemistry
 - Tumor markers (CEA and CA19-9)
- Obtain a urine sample for urinalysis
- Optional tumor biopsy sample (only if discontinuation due to disease progression)
- Assess compliance of encorafenib and/or binimetinib dosing and use of the dosing diary. Collect all remaining bottles of study drugs.
- Review concomitant medications/therapies
- Assess AEs since previous visit
- Obtain information on Healthcare Resource Utilization in case of hospitalization since previous visit (see **Section 8.7**)

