### 6.3.3. Exploratory endpoints

The following exploratory efficacy endpoints will be determined:

- Changes from baseline in blood tumor markers (carcinoembryonic antigen [CEA] and carbohydrate antigen 19-9 [CA19-9]) at the beginning of each cycle and at the end of treatment.
- *BRAF*V600E mutation status in blood circulating tumor DNA (ct-DNA) at baseline.
- MSI status in formalin-fixed paraffin-embedded (FFPE) samples via established PCR assays in tumor sample versus germline control at screening.

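### SAP Tables 2–7 define no End-of-treatment window, so end-of-treatment tumour markers and questionnaires are tabulated under another visit label or displaced

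*SAP*

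**What the plan says.** SAP Table 1 (section 6.4) gives End of treatment (901) and Safety follow-up (902) as separate labels for statistical output. SAP 6.3.3 defines the tumour-marker endpoint as change from baseline "at the beginning of each cycle and at the end of treatment".

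SAP 9.3, Tables 2–7, maps assessments to analysis windows. None of the six tables has an EOT row. Each ends with one post-treatment row, Safety follow-up, whose planned timing is "Post treatment study day 30" and whose range is "Last administration of study treatment day+1 to Post treatment study day 37". The cycle windows for the markers from Cycle 3 are "Study days k-13to k+14", with k the planned Day 1. They have no upper limit at last dose. Within a window, "the assessment closest to the planned visit is used in analyses by time window".

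Protocol 9.1.9 places the EOT visit no later than "14 days after the last dose of study treatment". Protocol 8.4.2.2 and 9.1.9 schedule CEA and CA19-9 at that visit; the 30-day visit (9.1.10.1) does not list them. QLQ-C30, EQ-5D-5L and PGIC are scheduled at both visits. The SAP tabulates the markers (section 17) and the questionnaires (sections 16.1–16.3) by time window, and counts completed and missing questionnaires per window (section 16).

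**The concern.** The windows decide which value appears under which visit in the descriptive tables. With no EOT row, no rule in 9.3 can produce an EOT result, although EOT is one of the two kinds of time point in the marker endpoint. Table 7 instead carries a row for a visit at which no marker is drawn.

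For the questionnaires, the follow-up row receives forms from two different visits and keeps one per subject. Its contents depend on who returned a later form, so it mixes forms completed soon after stopping treatment with forms completed about a month later. Its completion count is distorted too: a subject who skipped the 30-day form but completed the EOT form counts as having completed follow-up, and EOT completion is never shown. Change in quality of life is a secondary endpoint, and the protocol synopsis promises a summary at every visit.

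Because post-treatment values also lie in a cycle window, two programmers following the same text could label the same value differently, one of them as a treatment-cycle visit.

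**Working it through.** **Inputs.** Post-treatment day i is last-dose day + i (SAP Tables 2–7, footnote). The follow-up window is post-treatment days 1–37, planned day 30. The EOT visit is on days 0–14 (Protocol 9.1.9). The planned cycle day is k = (x−1)×28+1, with window k−13 to k+14 (Tables 2 and 7).

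**Check of the SAP's own bounds.** Cycle 2 has k = 29, and 29+14 = 43, the upper bound that Table 7 states. Cycle 3 has k = 57, giving days 44–71. Cycle 4 has k = 85, giving days 72–99. Enumerating study days 1–800 leaves no day outside a cycle window.

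**Tumour markers.**
- EOT on days 1–14: 14 of 14 days lie in the follow-up window, and all lie in a cycle window as well.
- EOT on day 0, the day of last dose: outside the follow-up window, which opens on day 1, so it lies only in a cycle window.
- Under neither reading is the value labelled End of treatment.

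*Illustration:* last dose on study day 84, EOT on day 91. The follow-up window is 84+1 = 85 to 84+37 = 121. The Cycle 4 Day 1 window is 72–99. Day 91 is in both.

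**Questionnaires in the follow-up window.** The distance of the EOT form from the planned day is 30−14 = 16 to 30−1 = 29 days.
- A 30-day form on days 27–33 is 0–3 days away. Over 14 EOT days × 7 follow-up days, the EOT form loses in 98 of 98 combinations.
- The result does not need day 27–33. A later form up to day 30 is nearer because it is later; one on days 31–37 is 1–7 days away, still less than 16. So any later form obtained by day 37 displaces the EOT form in this window.
- With no such form, the EOT form is the only candidate and is reported as Safety follow-up.

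**Effect of the 30-day visit's two definitions.** Protocol 9.1.10.1 times it about 30 days after last dose, or before new anticancer therapy if sooner. Flow-chart note q times it 30 days after EOT. If the second is counted from the EOT visit:
- EOT on days 1–7 gives a follow-up form on days 31–37, and the EOT form is displaced.
- EOT on days 8–14 gives a follow-up form on days 38–44, outside the window. The EOT form then takes the Safety follow-up label, and the true follow-up form falls only in a cycle window.

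**Which outputs use the windows.** The SAP text plans by-window summaries for CEA/CA19-9 (section 17), the three questionnaires and their completion (section 16), ECOG PS (15.7) and intraocular pressure (15.10). Coagulation, urinalysis, haematology and chemistry are summarised by worst grade or shift over the treatment period (15.3), which runs to last dose + 30 days (9.1.2) and so includes EOT values. Weight enters only as at least one notable change (15.4, Appendix 4).

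**The case against.** The other side has several sound points.

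- **Scope.** A reader might infer that every EOT assessment covered by Tables 2–7 is lost. The documents do not support this. The SAP text has no by-window table for weight, coagulation or urinalysis, and section 20 records that over-time safety analyses were removed. Worst post-baseline analyses ignore the windows.
- **Selection.** A reader might also infer that EOT quality of life disappears for the sickest, leaving only patients well enough to attend day 30. The closest-value rule works the other way: a subject with no later form keeps the EOT form. The defect is mixed timing under one label, not removal of the sickest.
- **Loss for everyone with a day-30 form.** This is too strong as well. An EOT form displaced from the follow-up window may still be the only candidate for a cycle window and appear there, mislabelled.
- **Other handling.** Table 1 gives EOT an output label, individual listings cover all analysed criteria, the marker–response analysis uses change to nadir, and the external list of tables cannot be seen here. The nadir and listings are indeed safe. But Table 1 attaches no window to visit 901, and section 17 explicitly tabulates the markers by window.
- **Importance.** SAP section 8 treats everything except the primary test as exploratory. No test or decision depends on this.

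What remains is a stated rule that, applied as written, gives a wrong label or drops a scheduled value from its row.

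**Conclusion.** The point holds within limits. As written, no by-window table can report CEA or CA19-9 at end of treatment. EOT values on days 1–14 qualify for both Safety follow-up and a cycle visit with no rule to choose, and EOT values on the last-dose day qualify only for a cycle visit. In the follow-up window, EOT questionnaires are displaced by any later form obtained by day 37 and are otherwise relabelled, so that row and its completion counts cannot be read as a 30-day result.

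The effect is confined to the by-window summaries of CEA/CA19-9, QLQ-C30, EQ-5D-5L and PGIC with their completion, ECOG PS and intraocular pressure. The primary confirmed response rate, the nadir and worst-value analyses and the listings do not change. The number of subjects affected cannot be derived from the documents; it depends on how many have an EOT visit on days 1–14 and a later form by day 37. The conclusion assumes that the windows in 9.3 are programmed as written and that the unseen table list does not override them. It is worth correcting because a named exploratory time point and a secondary quality-of-life endpoint are involved and the correction is cheap.

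**What to change.** 1. Add an End of treatment row, keyed to the eCRF EOT visit (901), to the tables for assessments collected at EOT. Keying to the visit is safer than a day range: a range starting the day after last dose would miss an EOT visit held on the last-dose day.
2. Reserve the Safety follow-up row for visit 902.
3. State that EOT-visit assessments, and any assessment after last dose, are not assigned to cycle windows.
4. Reconcile Protocol 9.1.10.1, which counts the 30-day visit from last dose, with flow-chart note q, which counts it from end of treatment, and align the follow-up window with the result.

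The cost is edits to the SAP tables, one clarification of visit timing and a re-run of descriptive outputs. No new data are needed.

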**Determination of Missing Adequate Tumor Assessments**

The term ‘adequate Tumor Assessments (TA)’ is defined as TA with overall lesion response different from missing and ‘Unknown’. The term ‘missing adequate TA’ is defined as TA not done or TA with overall lesion response equal to ‘Not Evaluable’. For the sake of simplicity, the ‘missing adequate TA’ will also be referred as ‘missing TA’. An exact rule to determine whether there is one or two missing TAs is therefore needed.

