17.6.5. Time point response

It is assumed that at each protocol specified time point, a response assessment occurs table 1 provides a summary of the overall response status calculation at each time point for subjects who have measurable disease at baseline.

Table 1- Time point response: subjects with target (± non-target) disease.			
Target lesions	Non-target lesions	New lesions	Overall response
CR	CR	No	CR
CR	Non-CR/non-PD	No	PR
CR	Not evaluated	No	PR
PR	Non-PD or not all evaluated	No	PR
SD	Non-PD or not all evaluated	No	SD
Not all evaluated	Non-PD	No	NE
PD	Any	Yes or No	PD
Any	PD	Yes or No	PD
Any	Any	Yes	PD

CR=complete response, PR=partial response, SD=stable disease, PD=progressive disease, NE=not evaluable

- **Missing assessments and not evaluable designation**

When no imaging/measurement is done at all at a particular time point, the subject is not evaluable (NE) at that time point. If only a subset of lesion measurements are made at an assessment, usually the case is also considered NE at that time point, unless convincing argument can be made that the contribution of the individual missing lesion(s) would not change the assigned time point response. This would be most likely to happen in the case of PD.

- **Best overall response: all time points**

The *best overall response* is determined once all the data for the subject is known.

Best response is defined as the best response across all time points (for example, a subject who has SD at first assessment, PR at second assessment, and PD on last assessment has a best overall response of PR). When SD is believed to be the best response, it must also meet the protocol specified minimum time from baseline. If the minimum time is not met when SD is otherwise the best time point response, the subject's best response depends on the subsequent assessments. For example, a subject who has SD at first assessment, PD at second and does not meet minimum duration for SD, will have a best response of PD. The same subject lost to follow-up after the first SD assessment would be considered not evaluable.

- **Special notes on response assessment**

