**This rule will be based on the distance between the last adequate TA date and the event date.**

Let D1 be the largest distance (relative to the last adequate TA date) that a patient can have a tumor assessment and not be classified as having missed an assessment. Let D2 be the largest distance (relative to the last adequate TA date) that a patient can have a tumor assessment and not be classified as having missed two assessments. If the distance exceeds threshold D1 or D2 then the analysis will assume one or two missing TAs, respectively.

The threshold D1 will be defined as the protocol specified interval between the TAs plus the protocol allowed window around the assessments. Similarly, the threshold D2 is defined as two

times the protocol specified interval between the TAs plus the protocol allowed window around the assessments.

As per protocol, post-screening assessments are expected to be performed every  $A=6$  weeks ( $\pm B=7$  days) from the first dose for the first 12 weeks of treatment ( $I=84$  days); except for first tumor evaluation for which the time-window allowed is day 42 +7 days from first dose, then every  $X=8$  weeks ( $\pm Y=7$  days) thereafter until disease progression, subject decision, withdrawal of consent, initiation of subsequent anticancer therapy, subject is lost to follow-up, death or defined end of study.

Therefore:

- if the last adequate tumor assessment before the event date is performed on or before study day 21 ( $=7*A/2$ ) then  $D_1=49 (=A*7+B)$  days and  $D_2=91 (=2*A*7+B)$  days;
  - This accounts for the scenario where the last adequate tumor assessment is the baseline assessment. This also allows for the rare instance where an additional assessment occurred early in the study.
- if the last adequate tumor assessment before the event date is performed between study day  $M+1$  (where  $M= I- (1.5*A)*7$ ) to study day  $N$  then  $D_1=A*7+2*B$  days and  $D_2=(A+X)*7+B+Y$  days;
  - Day  $N$  is calculated as  $N = I- (0.5*A)*7$ .
  - This accounts for the scenario where only the first scheduled assessments after the last adequate tumor assessment occur prior to month  $I$ .
- if the last adequate tumor assessment before the event date is performed between study day  $N+1$  and study day  $P$  then  $D_1=X*7+B+Y$  days and  $D_2=2*X*7+B+Y$  days;
  - Day  $P$  is calculated as  $P = I+ (0.5*X)*7$ .

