### **11.2. MISSING DATA (OTHER THAN DROP-OUT)**

#### **11.2.1. Missing efficacy data**

Missing values will not be substituted by estimated values but considered as missing in statistical analysis.

Note: For tumor assessment, when no imaging/measurement is done at all at a particular time point, the patient is not evaluable (NE) at that time point and will be analysed as such.

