#### **14.2.4. PFS based on investigator assessment**

PFS based on local review will be calculated and summarized using the KM method. The corresponding median PFS with 95% CI, 25th and 75th percentiles (Brookmeyer and Crowley 1982, Klein and Moeschberger 1997), as well as PFS estimated probabilities at selected time points (every 2 months up to 14 months) will be provided with 95% CI (Kalbfleisch and Prentice 2002) for the FAS and ES.

Progressive disease and death from any cause will be considered as events. If death or PD is not observed, the PFS will be censored at the date of last adequate tumor assessment prior to the cutoff date or new anti-tumoral treatment intake. However, if a PFS event is observed after more than 1 missing or inadequate tumor assessment, it will be censored at the last adequate tumor assessment. If a PFS event is observed after a single missing or non-adequate tumor assessment, the actual date of event will be used.

Censoring rules to be applied to the PFS endpoint are described in detail in

Table 12. Censor status will be summarized.

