**Table 12: Censoring rules for PFS**

In the below table, “new antineoplastic therapy” refers to any additional secondary antineoplastic medication or anti-cancer surgery or radiotherapy.

	Situation	Event Date	Outcome
No baseline tumor assessments			
A1	No baseline assessment and death after the second scheduled post-baseline tumor assessment, or no death	Date of first study treatment administration	Censored
A2	No baseline assessment and death on or before the second scheduled post-baseline tumor assessment	Date of death	Event
No post-baseline tumor assessments (without new antineoplastic therapy given)			
B1	Death on or before the second scheduled post-baseline tumor assessment	Date of death	Event
B2	Death after the second scheduled post-baseline tumor assessment or no death	Date of first study treatment administration	Censored
With baseline and post-baseline tumor assessments (without new antineoplastic therapy given prior progression or death without progression observed)			
C1	Progression with zero or one missed/inadequate tumor assessment prior to progression	Date of progression	Event
C2	Death but no progression, with zero or one missed/inadequate tumor assessment prior to death	Date of death	Event
D1	Progression but two or more consecutively missed/inadequate tumor assessments prior to progression	Date of last adequate tumor assessment*	Censored
D2	Death without progression, but two or more consecutively missed/inadequate tumor assessments prior to death	Date of last adequate tumor assessment*	Censored
E	No progression, no death	Date of last adequate tumor assessment*	Censored
F	Treatment discontinuation due to ‘Disease progression’ without documented progression, i.e. clinical progression based on investigator claim	N/A (not considered as an event, patient without documented PD should be followed for progression after discontinuation of treatment)	Information ignored
Initiation of new antineoplastic therapy given prior progression or death without progression observed			
G	New antineoplastic therapy started before progression or death	Date of last adequate tumor assessment prior to initiation of new antineoplastic therapy*	Censored
H	No post-baseline tumor assessment and new antineoplastic therapy started prior to a death	Date of first study treatment administration	Censored

\* tumor assessment with non-missing and non-unknown overall lesion response, as defined in section 9.3.

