#### **14.2.7. DOR based on investigator-assessed tumor evaluation**

Duration of response according to investigator will be calculated among the confirmed responders (i.e. CR and PR) from the time that measurement criteria are first met for complete or partial response (whichever status is recorded first) after first study treatment administration until the earliest date of progression or death due to underlying disease.

- Patients who are lost to follow-up, or reach the time point of analysis without a known record of progression or death will have the duration of response censored at the date of last adequate tumor assessment.

- Patients who received a new anti-tumoral treatment (chemotherapy, hormonotherapy, radiotherapy, surgery or other anti-tumoral treatment), whatever the type of treatment before their disease progression will be censored at their last adequate radiological assessment (i.e., at the date of last tumor assessment of CR, PR or SD).
- If an event is observed after a single missing or non-adequate tumor assessment, the actual date of progression will be used.
- If an event is observed after two or more missing or non-adequate tumor assessment, the duration of response will be censored at the date of last adequate tumor assessment.

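### SAP 9.3 calls a tumour assessment adequate if it is not missing and not Unknown, yet counts a Not Evaluable scan as missing; coded literally, this can alter PFS, DOR and TTR

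*SAP*

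**What the plan says.** SAP section 9.3 (Determination of Missing Adequate Tumor Assessments) gives two definitions in adjacent sentences. An adequate assessment "is defined as TA with overall lesion response different from missing and" *Unknown*. A missing adequate assessment "is defined as TA not done or TA with overall lesion response equal to" *Not Evaluable*. The footnotes of Tables 12 (PFS), 13 (PFS sensitivity), 14 (DOR) and 15 (TTR) carry the first definition forward: "tumor assessment with non-missing and non-unknown overall lesion response, as defined in section 9.3".

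The protocol's RECIST appendix (17.6.5) lists the time-point categories: "CR=complete response, PR=partial response, SD=stable disease, PD=progressive disease, NE=not evaluable". SAP Tables 10 and 11 use the same five. SAP 11.2.1 says that when no imaging is done "the patient is not evaluable (NE) at that time point and will be analysed as such".

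On counting missed scans, section 9.3 states: "This rule will be based on the distance between the last adequate TA date and the event date". For a PFS event after more than one missing or inadequate assessment, section 14.2.4 says "it will be censored at the last adequate tumor assessment". For DOR after two or more, section 14.2.7 says "the duration of response will be censored at the date of last adequate tumor assessment".

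**The concern.** The two definitions should be complementary, and as written they are not. *Unknown* is not one of the time-point categories, so excluding it excludes nothing, and an NE scan satisfies both definitions. The last adequate assessment does two jobs: it starts the D1/D2 distance, and it is the censoring date in Table 12 rows D1, D2, E and G and in the corresponding rows of Tables 13 to 15. Someone who codes from the footnotes and someone who codes from the second sentence of 9.3 can therefore give the same patient a different event status or censoring date for PFS, DOR or TTR.

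**Working it through.** **Reproducing Table 8.** Inputs from SAP 9.3: A = 6 weeks, B = 7 days, I = 84 days, X = 8 weeks, Y = 7 days.

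- Cut points: M = 84 − 1.5×6×7 = 21; N = 84 − 0.5×6×7 = 63; P = 84 + 0.5×8×7 = 112.
- Last adequate scan by day 21: D1 = 6×7 + 7 = 49; D2 = 2×6×7 + 7 = 91.
- Days 22 to 63: D1 = 6×7 + 2×7 = 56; D2 = (6+8)×7 + 7 + 7 = 112.
- Day 64 onward: D1 = 8×7 + 14 = 70; D2 = 2×8×7 + 14 = 126.

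These match Table 8. The three worked examples under it (distances 25, 55 and 92 days) give 0, 1 and 2 missed scans, as printed.

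**Comparing the two readings.** Scans are placed on the nominal schedule (days 42 and 84, then every 56 days: 140, 196, 252, and so on), with baseline taken as day 1. A visit with no scan is missing under both readings. Months are days/30.4375 (SAP 9.1.3).

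| Sequence | NE not adequate | NE adequate (literal) |
|---|---|---|
| SD 84, NE 140, PD 196 | 196−84 = 112 ≤ 126: event day 196 | 196−140 = 56 ≤ 126: event day 196 |
| SD 84, NE 140, NE 196, PD 252 | 252−84 = 168 > 126: censored day 84 (2.76 months) | 252−196 = 56 ≤ 126: event day 252 (8.28 months) |
| SD 42, NE 84, no scan 140, PD 196 | 196−42 = 154 > 112: censored day 42 (1.38 months) | 196−84 = 112 ≤ 126: event day 196 (6.44 months) |
| SD 84, NE 140, no event | censored day 84 | censored day 140: 56 days later (1.84 months) |

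**Event status.** One isolated NE followed by PD at the next visit gives the same event date under both readings. Two consecutive lost visits were tried in the orders NE then no scan, no scan then NE, and NE then NE, with the last evaluable scan at day 1, 42, 84 or 140. Status differed in all 3×4 = 12 patterns.

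**DOR.** Take PR on days 42 and 84, NE on days 140 and 196, and PD on day 252. DOR is an event at 252−42+1 = 211 days under the literal reading, and is censored at 84−42+1 = 43 days otherwise.

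**Censoring dates without an event.** One trailing NE moves PFS censoring later by 41 to 56 days (1.35 to 1.84 months). Two trailing lost visits ending in an NE move it by 83 to 112 days (2.73 to 3.68 months). The same shift applies to TTR for a non-responder without a PFS event (Table 15 row C2). If every post-baseline scan is NE, PFS is censored at first dose under one reading and at the last NE scan under the other.

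**The case against.** The strongest reply is that *Unknown* is only an older label for NE and that the intent is plain. The second sentence of 9.3 expressly puts an NE scan among the missing ones. Sections 14.1 and 14.2.2 speak of unknown status in patients classed as Non-Evaluable. The SAP version history records the move from one term to the other, which is evidence of meaning only. Table 12 counts missed or inadequate assessments and section 14.2.4 missing or inadequate ones, with both terms referred back to 9.3. Read this way, two NE scans before a PD fall under row D1 and the patient is censored. This stands as evidence of intent. It does not make the written definition and four footnotes correct: they are operative rules, and they are what a programmer or independent validator would follow.

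Several limits on the effect also stand:

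- A reader might infer that every censoring date depends on the last adequate scan. It does not. Table 12 rows A1, B2 and H and Table 15 rows C1 and D1 censor at first dose, Table 15 row B censors at maximum follow-up, and OS does not use the term.
- DOR censoring for a responder without PD or death (6.3.2), or at new therapy (14.2.7), is already tied to a scan of CR, PR or SD. The Table 14 footnote does not match that, so DOR exposure is mainly through the two-missed-scans rule.
- The PFS sensitivity analysis (Table 13) counts the event however many scans were missed, so it is immune on event status, though not on censoring dates.
- SAP section 8 treats every result other than the primary test as exploratory.

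**Conclusion.** The definition is wrong as written and should be corrected, although the intended rule is reasonably clear. If NE is programmed as not adequate, no result changes. If the definition and footnotes are programmed literally, main-analysis PFS and DOR event status changes only where at least two consecutive visits are lost and at least one is NE. Trailing NE scans move PFS and TTR censoring later by about one to two scan intervals. These sizes assume nominal visit days and baseline at day 1.

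A reader might infer that the PFS or DOR results are in fact wrong, or that the primary conclusion is at risk. The documents support neither. They do not show how the rule was programmed, and they give neither an NE rate nor the eCRF response list, so the number of patients affected cannot be stated. cORR rests on the explicit NE rules of Table 10, and the sample size does not use the term at all.

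**What to change.** In SAP 9.3, define an adequate tumour assessment as one with an overall lesion response of CR, PR, SD or PD, so that a missing or NE response is not adequate. Change the footnotes of Tables 12, 13, 14 and 15 to: *tumor assessment with overall lesion response of CR, PR, SD or PD, as defined in section 9.3*. Putting *Not Evaluable* in place of *non-unknown* in the footnotes would reverse their meaning, so list the categories instead. Then check that the PFS, DOR and TTR programs follow the definition. The cost is five short text edits and one program check; no data collection changes.
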